7.1.2. PK vs Efficacy

The relationship between serum guselkumab and/or golimumab concentrations and efficacy endpoints may be explored, e.g.:

1. The relationship between serum guselkumab and golimumab concentrations (quartiles) and clinical response, clinical remission, change in Mayo score, symptomatic remission, and endoscopic healing status at Week 12 and Week 38 may be explored by treatment group.

2. The relationship between serum guselkumab and golimumab concentrations (quartiles) and change from baseline in CRP concentration (mg/L) and Fecal Calprotectin concentration (mg/kg) at Week 12 and Week 38 may be explored by treatment group.

7.1.3. Population PK Analysis

When appropriate, population PK analysis will be performed using serum guselkumab concentration-time data in PK analysis set with the nonlinear mixed-effects modeling (NONMEM) approach. Population PK analysis for golimumab may also be explored when appropriate. Details will be provided in a separate document.

7.2. Immunogenicity

Immunogenicity analyses will be based on the Immunogenicity Analysis Set (Section 2.2.5). Participants will be analyzed according to the study intervention that they actually received. No imputation for missing data will be performed.

7.2.1. Antibodies to Guselkumab and to Golimumab

Blood samples will be collected to examine the formation of antibodies to guselkumab and/or to golimumab at the specified visits as shown in the SoA (Protocol Section 1.3). Serum samples will also be collected at the final visit from participants who terminate study participation early.

The antibodies to guselkumab and/or to golimumab status (positive at any time, negative) and peak titers will be summarized by treatment group through Week 12 and through Week 38.

A listing of participants who are positive for antibodies to guselkumab and/or to golimumab will be provided. The sample antibodies status, the titer, and the neutralizing antibodies status will be listed by visit. This listing will also provide information regarding dose administered, injection-site reactions and/or reactions temporally associated with infusion, guselkumab and/or golimumab serum concentration, partial Mayo score, and Mayo score for all visits. In addition, a list of antibodies to guselkumab and/or to golimumab status in participants who discontinued study agent early will be provided.

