1.3. Schedule of Activities (SoA)

Table 1: SoA - Combination Comparison Phase (ie, through Week 12)									
	Phase	Screening	Treatment						
	Week	Within 8 weeks	W0	W2	W4	W6 ^e	W8	W10	W12 ^f
Study Procedures^{a,b,c,d}									
Screening/Administrative									
Informed consent (ICF) ^g		X							
ICF for optional pharmacogenomic sub-study ^g		X							
ICF for optional Week 4 endoscopy and biopsy sub-study ^g		X							
Review medical history requirements		X							
Inclusion/exclusion criteria ^h		X	X						
Demographics		X							
Prestudy therapy		X							
Preplanned surgery/procedure(s)		X							
QuantiFERON [®] -TB test ⁱ		X							
HBV and HCV testing		X							
HIV test		X							
Chest radiograph ^j		X							
Serum pregnancy test ^k		X							
Stool for enteric pathogens ^l		X							
Training on Mayo diary and BSFS diary completion ^m		X	X						
Study Intervention Administration									
Randomization			X						
Administer study intervention			X ^z	X	X	X	X	X	
Efficacy Evaluations									
Endoscopy ⁿ		X ^o			(X) ^p				X
Mayo score			X						X
Partial Mayo score		X		X	X	X	X	X	
BSFS			X	X	X	X	X	X	X
Patient-Reported Outcomes (PROs)^b									
IBDQ			X			X			X
PROMIS-29			X			X			X

Table 1: SoA - Combination Comparison Phase (ie, through Week 12)									
	Phase	Screening	Treatment						
	Week		W0	W2	W4	W6 ^e	W8	W10	W12 ^f
Study Procedures^{a,b,c,d}									
PROMIS Fatigue Short Form 7a			X				X		X
PGIC						X			X
Safety Evaluations									
Physical examination		X							X
12-lead ECG		X							
TB evaluation ^l /Other infection assessment ^l		X	X	X	X	X	X	X	X
Vital signs ^f		X	X	X	X	X	X	X	X
Weight		X	X						X
Height		X							
Urine pregnancy test ^k			X	X	X	X	X	X	X
Concomitant therapy review		X	X	X	X	X	X	X	X
Adverse events		X	X	X	X	X	X	X	X
UC-related emergency department visits, hospitalizations, and surgeries			X	X	X	X	X	X	X
Injection-site evaluation ^{bb}			X	X		X		X	X
C-SSRS ^s		X	X	X	X	X	X	X	X
Clinical Laboratory Tests									
Hematology and chemistry ^{aa}		X	X	X	X	X	X	X	X
CRP			X	X	X	X	X	X	X
Fecal calprotectin			X	X	X		X		X
Pharmacokinetics/Immunogenicity^t									
Serum guselkumab/golimumab concentration			X	X	X	X	X	X	X
Antibodies to guselkumab/golimumab			X	X	X		X		X
Pharmacodynamics and Biomarkers									
Biopsy (RNA, histology, single cell isolation) ^u		X ^v			(X) ^p				X
Serum biomarkers ^w		X		X	X				X
Whole blood (RNA) ^w		X		X	X				X
Whole blood (PBMC) ^{w,cc}		X			(X) ^p				X
Fecal biomarkers ^x			X	X	X				X
Pharmacogenomics									

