
Table 1: SoA - Combination Comparison Phase (ie, through Week 12)									
	Phase	Screening	Treatment						
	Week	Within 8 weeks	W0	W2	W4	W6 ^c	W8	W10	W12 ^f
Study Procedures ^{a,b,c,d}									

assessments) may be performed at the investigator’s clinical discretion.
 
m. Participants should be instructed to bring their diaries to each study visit for review.
 
n. Endoscopy findings will be assessed by the investigator (ie, local endoscopist) during the procedure and a video of the endoscopy must be submitted to the central reader.
 
o. The screening endoscopy must be performed within 2 weeks of the baseline (W0) visit. The interval from the endoscopy procedure to the availability of the Mayo endoscopy subscore is approximately 4 days; therefore, the screening endoscopy must be performed at least 4 days before the baseline (W0) visit. The Mayo endoscopy subscore obtained during the central review of the video endoscopy will be used to determine eligibility (ie, Mayo endoscopy subscore ≥ 2) and to calculate the baseline Mayo score. A full colonoscopy will replace a sigmoidoscopy if screening for polyps or dysplasia is required. At least 48 hours must elapse between a colonoscopy with polypectomy and the W0 visit.
 
p. Only those participants who consent to participate in the optional endoscopy and biopsy sub-study will undergo Week 4 endoscopy and mucosal biopsy collection and whole blood PBMC collection.
 
q. If TB is suspected at any time, a chest radiograph (or chest CT scan if obtained instead) and QuantiFERON[®]-TB test should be performed. In countries where the QuantiFERON[®]-TB test is not registered/approved or the tuberculin skin test is mandated by local health authorities, TB skin testing (see Appendix 3 [Section 10.3]) should also be performed. Note: In Ukraine, while the QuantiFERON[®]-TB test is not approved/registered, it is accepted and a tuberculin skin test is not required.
 
r. Temperature, pulse/heart rate, respiratory rate, and blood pressure. At a study intervention administration visit, vital signs should be obtained before, approximately every 30 minutes during, and twice (at approximately 30-minute intervals) after completion of the IV infusion(s), or before and approximately 30 minutes after the SC injection, or if the participant reports any symptoms.
 
s. At the screening visit, the C-SSRS should be completed as the first assessment after signing informed consent and before any other tests, procedures, or other consultations. For subsequent visits, the C-SSRS should be completed after all PROs and before any other tests, procedures, or other consultations.
 
t. For all visits where study intervention will be administered, 1 blood sample should be collected prior to study intervention administration for evaluation of serum concentrations and/or antibodies to interventions. In addition, for IV infusion-related visits (ie, Weeks 0, 4, and 8), another blood draw should be taken approximately 60 minutes after completion of the infusion for serum concentration measurement. All reasonable attempts should be made to collect samples at the scheduled timepoints and record the actual dates and times of PK sample collections.
 
u. Mucosal biopsy samples will be collected from all participants during endoscopy for RNA expression analysis, histologic assessment, and single cell isolation.
 
v. The screening biopsy samples for histology, RNA analyses, and single cell isolation will be collected from all participants during the screening endoscopy performed within 2 weeks of the baseline (W0) visit.
 
w. Serum biomarkers and whole blood RNA and PBMCs will be collected from all participants to evaluate the molecular
									

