9.4.3. Other Analyses

Pharmacokinetic Analyses

Serum guselkumab and golimumab concentrations over time will be summarized for the PK Analysis Set. Descriptive statistics, including arithmetic mean, SD, median, interquartile range, minimum, and maximum will be calculated at each nominal sampling timepoint. All concentrations below the lowest quantifiable concentration or missing data will be labeled as such in the concentration database or data presentations. Concentrations below the lowest quantifiable concentration will be treated as zero in the summary statistics.

Participants will be excluded from the PK analysis if their data do not allow for accurate assessment of the PK (eg, incomplete administration of the study intervention; missing time of study intervention administration). Detailed rules for the analysis will be specified in the SAP.

Population PK modeling may be conducted when appropriate. If these population PK analyses are conducted, the results of these analyses will be presented in a separate report.

Immunogenicity Analyses

The incidence of antibodies to guselkumab and to golimumab will be summarized for all participants who receive at least 1 dose of guselkumab or golimumab and have appropriate samples for detection of antibodies to guselkumab and to golimumab (ie, participants with at least 1 sample obtained after their first dose of guselkumab or golimumab, respectively).

A listing of participants who are positive for antibodies to guselkumab and to golimumab will be provided, respectively. The maximum titers of antibodies to guselkumab and to golimumab will be summarized for participants who are positive for antibodies to guselkumab and to golimumab, respectively.

The incidence of neutralizing antibodies to guselkumab and to golimumab will be summarized for participants who are positive for antibodies to guselkumab and to golimumab and have samples evaluable for neutralizing antibodies to guselkumab and to golimumab, respectively.

Pharmacokinetic/Pharmacodynamic Analyses

The relationship between serum concentrations of guselkumab and golimumab and the efficacy measures and/or relevant biomarker(s) may be explored graphically when appropriate. Additional analysis may be conducted if deemed necessary.

Biomarkers Analyses

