2.2.5. Immunogenicity Analysis Set

The immunogenicity analysis set is defined as all participants who receive at least 1 (partial or complete) dose of guselkumab and/or golimumab and have appropriate samples for detection of antibodies to guselkumab and/or to golimumab (ie, participants with at least 1 sample obtained after their first dose of guselkumab or golimumab, respectively). Participants in the Immunogenicity Analysis Set will be analyzed according to the study intervention they actually received.

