7.2.2. Antibody vs PK/Efficacy/Safety

To explore the relationship between antibodies to guselkumab status and to golimumab status and serum guselkumab and serum golimumab concentrations, and efficacy and safety, the following analyses may be performed as appropriate:

- Plots of median trough serum guselkumab concentrations over time by antibodies to guselkumab status

- Plots of median trough serum golimumab concentrations over time by antibodies to golimumab status
- Summary of clinical response, clinical remission, change in Mayo score, and endoscopic healing, all at Week 12 and Week 38, by antibodies to guselkumab and to golimumab status if sufficient participants have antibodies
- Summary of injection-site reactions by antibodies to guselkumab and to golimumab status
- Summary of AEs temporally associated with infusion by antibodies to guselkumab

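### SAP 7.2.1 classes antibody status without reference to the pre-dose Week 0 sample, so the antibody summary may include pre-existing reactivity

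*SAP*

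**What the plan says.** **Purpose.** SAP 7.2.1 opens: "Blood samples will be collected to examine the formation of antibodies to guselkumab and/or to golimumab at the specified visits". Protocol 9.4.3 uses the term incidence: "The incidence of antibodies to guselkumab and to golimumab will be summarized for all participants". It also plans a summary of maximum titers.

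**Status rule.** SAP 7.2.1 has two classes; antibody "status (positive at any time, negative) and peak titers will be summarized by treatment group through Week 12 and through Week 38". 

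**Sampling.** The row "Antibodies to guselkumab/golimumab" in Table 1 of Protocol 1.3 is marked at Weeks 0, 2, 4, 8 and 12. Footnote t says of dosing visits that "1 blood sample should be collected prior to study intervention administration for evaluation of serum concentrations and/or antibodies to interventions". The additional draw after an infusion is for serum concentration only, so the Week 0 antibody sample is pre-dose.

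**Analysis set.** SAP 2.2.5 requires appropriate samples, explained as "participants with at least 1 sample obtained after their first dose of guselkumab or golimumab, respectively".

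**Later use of status.** SAP 7.2.1.1 summarizes neutralizing antibodies among antibody-positive participants. SAP 7.2.2 looks at concentration, efficacy and reactions by antibody status, where "the following analyses may be performed as appropriate".

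**The concern.** Formation and incidence both describe something new since treatment began. A class that is met by a positive result at any visit does not measure that when one of the visits precedes the first dose. Immunogenicity of the combination is a secondary objective in both study phases, and the antibody table is its main summary. If some participants react in the assay before they have received either drug, the table may show pre-existing and new reactivity as one number, and a titer that was there at Week 0 may be reported as the peak. The same status would then define the denominator in 7.2.1.1 and, if those analyses are run, the groups in 7.2.2. Where few participants are positive, one or two such cases would be a visible part of the group.

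**Working it through.** The plan states no antibody rate, so there is no figure to reproduce. The check is a reading of the rules, followed by an illustration of scale.

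**1. Does any rule compare status with Week 0?** No. SAP 2.2.5 decides who is analyzed; it does not say which of their samples set the status or the peak titer. SAP 2.5 gives a general baseline definition but nothing links it to antibody status. Neither document defines treatment-emergent, induced or boosted antibodies, or a titer-rise rule. By contrast, SAP 6.2 plans change-from-baseline summaries and shift tables for laboratory values, and SAP 6.3.1 plans a shift table for the suicidality scale.

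**2. How is each pattern classed?**

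| Week 0 | After first dose | Literal any-time reading | Post-dose samples only | Compared with Week 0 |
|---|---|---|---|---|
| Negative | Negative | Negative | Negative | Negative |
| Negative | Positive | Positive | Positive | Treatment-emergent |
| Positive | Negative | Positive | Negative | Week 0 positive, unboosted |
| Positive | Positive, no titer rise | Positive | Positive | Week 0 positive, unboosted |
| Positive | Positive, titer rise | Positive | Positive | Treatment-emergent (boosted) |

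The readings part in rows three and four. The post-dose reading repairs row three but not row four.

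**3. Scale of one case.** With 70 planned per arm (Protocol 9.2), one participant is 1/70 = 1.4 percentage points. By Week 12, 70 + 70 = 140 participants are planned to receive each drug.

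**4. Illustration with assumed rates.** Let b be the share positive before dosing and e the share of Week 0 negatives who become positive. Neither is in the documents; I take b from 1% to 10% and e from 2% to 20%, and assume no boosting.

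- Any-time rate = b + (1 − b)e. Newly positive rate = (1 − b)e. The difference is b.
- Pre-existing share of those called positive = b / [b + (1 − b)e].
- b = 1%, e = 5%: 0.01 + 0.99 × 0.05 = 5.95% against 4.95%; share 0.01/0.0595 = 17%.
- b = 5%, e = 5%: 0.05 + 0.95 × 0.05 = 9.75% against 4.75%; share 0.05/0.0975 = 51%.
- Ends of the range: b = 1%, e = 20% gives 0.01/0.208 = 5%; b = 10%, e = 2% gives 0.10/0.118 = 85%.
- Post-dose samples only, with half of the Week 0 positives persisting: b(0.5 + 0.5e) + (1 − b)e. At b = e = 5% this is 0.05 × 0.525 + 0.0475 = 7.4%, which is 2.6 points above the newly positive rate.
- Chance of at least one Week 0 positive at b = 1%: 1 − 0.99^70 = 51% in one arm and 1 − 0.99^140 = 76% among those given one drug.

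The span from 5% to 85% shows that the share cannot be estimated from the documents.

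**The case against.** The strongest reply is that status should be read from post-dose samples. Both documents tie appropriate samples to those taken after the first dose, and SAP 7.2 bases all immunogenicity analyses on that set. On this reading a Week 0-only positive is not counted and a pre-dose titer cannot be the peak. That is a fair reading, but the text does not state it, and the persistent, unchanged baseline positive still counts.

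Other points stand as limits on the concern:

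- **The listing.** For positive participants, SAP 7.2.1 adds: "The sample antibodies status, the titer, and the neutralizing antibodies status will be listed by visit". A Week 0 positive could be seen there, although the summary table would not separate it.
- **Prior exposure.** Protocol 5.2 excludes anyone who has received a biologic against TNF or against IL-12 and/or IL-23, which includes both study drugs. Antibodies from earlier exposure to either drug are therefore unlikely, and natural or assay reactivity is what remains.
- **Optional comparisons.** The analyses in 7.2.2 are exploratory, and the efficacy summary there depends on enough participants having antibodies.

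A reader might go further and infer that any real association in 7.2.2 would be diluted. The documents do not support that. The analyses may not be run, and a participant with antibodies throughout could have altered exposure whatever their origin, so grouping by any positive result is defensible for a concentration comparison.

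**Conclusion.** The point holds as a gap in the status rule. The plan measures antibody formation with a class that ignores the baseline sample it collects, so the summary may include pre-existing reactivity under either reading of the text. A reader might infer that pre-existing reactivity is being reported as caused by the drug. The SAP does not say so: its categories are descriptive, it nowhere labels positives as induced, and it does not state that the Week 0 result enters the count.

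The size is unknown. The only figure that follows from the documents is 1.4 points per participant in an arm of 70; every rate in the illustration is assumed. The antibody status summary carries no hypothesis test, and the primary, major secondary and other efficacy conclusions are unaffected. This is a cheap improvement, not a serious defect.

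**What to change.** Amend SAP 7.2.1 to state how the Week 0 result is used:

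1. For each drug, define treatment-emergent positive as either Week 0 negative with a positive sample after the first dose of that drug, or Week 0 positive with a post-dose titer rise above a threshold that the sponsor pre-specifies for its assay. The documents give no titer precision or dilution scheme, so no particular cut-off can be taken from them.
2. Report the number of Week 0-positive participants separately, by treatment group.
3. Take peak titer from post-dose samples only.
4. Use this status in 7.2.1.1 and 7.2.2. Show unboosted Week 0 positives as their own category; pooling them with the negatives would contaminate the comparison group.

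The cost is SAP wording and one more category in the tables. The Week 0 sample is already scheduled, and Protocol 8.5.4 already reports titers for confirmed positive samples, so no new data are needed. The reported incidence may be slightly lower.

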7.2.1.1. Neutralized Antibodies to Guselkumab and to Golimumab

The incidence of neutralizing antibodies (NAbs) to guselkumab and/or to golimumab will be summarized through Week 12 and through Week 38 for participants who are positive for antibodies to guselkumab and/or to golimumab, respectively, and have samples evaluable for NAbs to guselkumab and/or to golimumab.

7.2.2. Antibody vs PK/Efficacy/Safety

To explore the relationship between antibodies to guselkumab status and to golimumab status and serum guselkumab and serum golimumab concentrations, and efficacy and safety, the following analyses may be performed as appropriate:

- Plots of median trough serum guselkumab concentrations over time by antibodies to guselkumab status

- Plots of median trough serum golimumab concentrations over time by antibodies to golimumab status
- Summary of clinical response, clinical remission, change in Mayo score, and endoscopic healing, all at Week 12 and Week 38, by antibodies to guselkumab and to golimumab status if sufficient participants have antibodies
- Summary of injection-site reactions by antibodies to guselkumab and to golimumab status
- Summary of AEs temporally associated with infusion by antibodies to guselkumab

7.3. Pharmacokinetic/Pharmacodynamic Relationships

If data permit, the relationships between serum guselkumab and serum golimumab concentration and efficacy may be analyzed graphically. If any visual trend is observed, a suitable population PK/PD model may be developed to describe the exposure-response relationship. Details will be given in a population PK/PD analysis plan and results of the population PK/PD analysis will be presented in a separate technical document.

8. BIOMARKERS

The biomarker analyses will characterize the effects of guselkumab and/or golimumab to identify biomarkers relevant to treatment, and to determine if these biomarkers can predict response to guselkumab or golimumab. Results of serum, stool, whole blood, and mucosal biopsy analyses will be reported in separate technical reports.

Changes in serum protein analytes, fecal biomarkers, and biopsy and whole blood RNA obtained over time will be summarized by study intervention. Associations between baseline levels and changes from baseline in selected markers and response to treatment will be explored. Biomarker analyses will be summarized in a separate technical report.

9. MEDICAL RESOURCE UTILIZATION AND HEALTH ECONOMICS

Medical resource utilization evaluations, including but not limited to UC-related emergency department visits, hospitalizations, and surgeries are collected in this study. The following is a list of the endpoints to be analyzed:

- Proportion of participants having any UC-related ER/hospitalizations/surgeries through Week 12 and through Week 38 (final safety follow-up)
- Proportion of participants with a UC-related hospitalization through Week 12 and through Week 38 (final safety follow-up)
- Proportion of participants with a UC-related surgery through Week 12 and through Week 38

The health economics data will be analyzed based on the FAS (Section 2.2.2) according to randomized study intervention regardless of the study intervention actually received.

The ICEs in categories 1 - 5 specified in Section 5.3.2 will not be used. No imputation will be performed for missing data and the missing values will remain as missing.

Treatment comparisons will be performed. Nominal p-values will be reported. These endpoints will not be adjusted for multiplicity.

Binary endpoints will be summarized with the number and frequency of participants by treatment group. Treatment comparisons (combination therapy versus each monotherapy) will be performed using a CMH chi-square test stratified by corticosteroid use at baseline (yes, no). In case of rare events, the Fisher's exact test will be used for treatment comparisons.

REFERENCES

1. Abraham BP and Kane S. Fecal Markers: Calprotectin and Lactoferrin. *Gastroenterol Clin N Am*. 2012;41:483-495.
